Study Design:	
The study aims to assess the safety and feasibility of oral nitrite in adults with hypertension and metabolic syndrome.
 
Subjects will undergo a screening visit to determine that eligibility requirements are met. Prior to receiving the study drug, subjects will be scheduled within 4 weeks of screening for a baseline assessment.
 
Subjects who meet the Inclusion Criteria and none of the Exclusion Criteria will be provided study drug. The study population (n=30) will receive oral sodium nitrite for 12 weeks:
 
Drug: oral formulation of sodium nitrite 40 mg three times daily or TID (once in the morning and again in the early afternoon and again in the evening).

	
Subjects will be evaluated as an outpatient with the first dose of study drug. Blood pressure, heart rate, methemoglobin levels and plasma nitrate and nitrite will be measured in the first two hours after dosing. Every other week safety visits will occur to assess adverse events (AE), methemoglobin level, interval histories, brief physical exams, medication compliance review and dispensing of study drug. Interval histories and physical exams will be obtained by a study investigator.
 
Subjects will also be contacted by the study investigator and/or the study coordinator for a follow-up assessment on Week 16 by telephone.

Planned Sample Size:	30 subjects
Duration of Treatment:	12 weeks
Major Inclusion Criteria:	
 • Age 18-60 years • BMI ≥ 30 kg/m² • Hypertension: defined as systolic blood pressure ≥ 130 and/or diastolic blood pressure ≥ 85 mm Hg at screening • Waist circumference: >102 cm in men, >88 cm in women

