1.2 SPECIFIC AIMS

Hypothesis:

Oral supplementation with sodium nitrite will result in improvement in insulin sensitivity, reduction in blood pressure, and improvement in endothelial and mitochondrial function, arterial stiffening, and microvascular inflammation, in overweight/obese adult subjects with metabolic syndrome and hypertension with limited toxicity in the dose proposed.

Specific Aims:

Aim 1: To examine the effect of oral nitrite on insulin sensitivity and mitochondrial function in overweight/obese adults with metabolic syndrome and hypertension.

Aim 2: To examine the effect of oral nitrite on blood pressure in overweight/obese adults with metabolic syndrome and hypertension.

Aim 3: To examine the effect of oral nitrite on endothelial function, arterial stiffening, and microvascular inflammation in overweight/obese adults with metabolic syndrome and hypertension.

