2. RESEARCH DESIGN AND METHODS

2.1 CLASSIFICATION AND METHODOLOGICAL DESIGNS

The study is a 12 week open-label, single-center, non-randomized drug treatment study of overweight adults with metabolic syndrome and hypertension.

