2.6 STATISTICAL ANALYSIS

Primary endpoint sample size estimates: To develop sample size estimates, we hypothesize that inorganic nitrite will have significant but perhaps slightly less robust effects compared to a 4-month supervised exercise weight loss intervention. We anticipate an effect size (improvement) in insulin stimulated glucose uptake of ~ 1.68 mg/min/kg fat free mass (FFM) with dietary nitrite. This represents just 60% of the effect size we have observed with diet and exercise (based on a mean

improvement in insulin sensitivity from 6.70 ± 2.0 (SD) to 9.51 ± 2.5 mg/min/kg FFM; n=25). This would provide 80% power to detect this conservatively-estimated smaller effect size in 30 subjects at a p value of 0.05.

Primary and secondary endpoint analyses: Repeated measures ANOVA with visit (pre-, post-treatment) as the within-subject effect will be used to evaluate response to treatment for primary and secondary endpoint measures of insulin sensitivity, mitochondrial function (muscle and platelet ROS generation, mitochondrial efficiency, and uncoupling by various platelet and muscle biopsy samples), BP, methemoglobin %, endothelial function (FMD), body weight, arterial stiffening (PWV), arterial thickening (IMT), glucose tolerance (HbA1C), blood markers of inflammation and vascular dysfunction, substrate oxidation (indirect calorimetry), cardiorespiratory fitness (maximal exercise tolerance test), and body composition (whole body DEXA for total body fat). Data will be presented as the mean \pm standard error for continuous variables. Transformations will be considered for data demonstrating non-normal distributions.

An interim statistical analysis is planned following completion of the 10th subject. If there is a statistically significant change in the primary outcome measure of insulin sensitivity with $p < 0.001$, discontinuation of the trial will occur. If $p > 0.001$, the trial will continue. Based on an extremely low p value to stop the trial, there will be no need to adjust final significance level.

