5.4 DATA SAFETY MONITORING PLAN

5.4.1 Data Safety Monitoring Board

The local Data Safety Monitoring Board (DSMB) will be comprised of members including experts in endocrinology, exercise physiology, clinical research, and clinical trial design, biostatistics, and research ethics. The DSMB will conduct interim monitoring of accumulating data from research activities to assure the continue safety of human subjects, relevance and appropriateness of the study, and the integrity of research data.

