- The frequency of monitoring that took place during the renewal intervals and/or the dates that data and safety monitoring was conducted.
- A summary of cumulative data related to unanticipated problems (including adverse events) including a determination of causality and whether the risk to benefit assessment has changed.
- If appropriate, a summary of pertinent scientific literature reports, therapeutic developments, or results of related studies that may have an impact on the safety of study participants or the ethics of the research study.
- A summary of the outcome of reviews conducted to ensure subject privacy and research data confidentiality.
- Final conclusions regarding changes to the anticipated benefit-to-risk assessment of the study participation and final recommendations related to continuing, changing, or terminating the study.

Stopping Rule:

For safety reasons, we propose to discontinue this study protocol once 2 subjects enrolled experience one of two of the following on repeat PK testing despite appropriate nitrite dose reduction as follows:

1. Methemoglobin greater than 5%. A nitrite dose reduction is proposed from 40 mg three times daily to 20 mg three times daily if this methemoglobin % is reached at any study visit. Two hour PK testing will be repeated on a separate day at the lower nitrite dose once two subjects have reached this initial methemoglobin threshold. If methemoglobin is greater than 5% on the lower nitrite dose, participation in the study for the subject will be discontinued.
2. Mean arterial pressure (MAP) decrease <55 mmHg, or if subject's baseline MAP is <60, and there is a decrease greater than or equal to 20% from their baseline (on the morning of receiving study drug). A nitrite dose reduction is proposed from 40 mg to 20 mg three times daily if this MAP threshold is reached. Two hour PK testing will be repeated on a separate day at the lower nitrite dose once two subjects have reached this initial MAP threshold. If MAP remains <55 mmHg or in the case of the subject with a baseline MAP <60, then if MAP decrease is greater than or equal to 20% from baseline on the lower dose, subject participation in the study will be discontinued.
3. Positive pregnancy test.

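### Should the early stop for a significant change in insulin sensitivity be advisory instead of mandatory?

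*Combined protocol and SAP*

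**What the plan says.** Section 2.6 schedules one interim analysis, when the tenth subject has completed. "If there is a statistically significant change in the primary outcome measure of insulin sensitivity with" p<0.001, "discontinuation of the trial will occur"; otherwise the trial goes on, and the final test keeps its 0.05 level. The trigger is the primary endpoint alone, and the direction of the change is not specified.

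Section 2.1 describes a "12 week open-label, single-center, non-randomized drug treatment study". The Synopsis gives a wider purpose ("The study aims to assess the safety and feasibility of oral nitrite"), and Section 1.2 lists further aims on blood pressure ("Aim 2: To examine the effect of oral nitrite on blood pressure in overweight/obese adults") and on vascular function. Under Section 5.4.1, "The DSMB will conduct interim monitoring of accumulating data from research activities", and the report described in Section 5.4.2 includes "final recommendations related to continuing, changing, or terminating the study". Neither section mentions the p<0.001 rule. The sample size in Section 2.6 is derived for insulin sensitivity only.

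**The concern.** An early stop for efficacy usually protects subjects on an inferior comparator, and this trial has no comparator. A crossing on the clamp result would end recruitment for every other aim at about a third of the planned sample. The primary estimate from a trial that stops on a very small p value also tends to be too high. Since the protocol already has a DSMB, it seems natural to let that board decide and to continue to 30 by default. Three things are at stake: precision for blood pressure, FMD, PWV and mitochondrial endpoints; the amount of safety data; and an inflated primary estimate.

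**Working it through.** **Inputs (Section 2.6).** "improvement in insulin sensitivity from 6.70 ± 2.0 (SD) to 9.51 ± 2.5 mg/min/kg FFM", from 25 subjects on diet and exercise; planned effect 1.68, about 60% of that change; 30 subjects; alpha 0.05, taken as two-sided. The pre-post correlation r is not given, so 0, 0.5, 0.7 and 0.8 are assumed.

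**1. The plan's own power.** 9.51 − 6.70 = 2.81, and 0.6 × 2.81 = 1.69, close to 1.68. The SD of the change is √(2.0² + 2.5² − 2r × 2.0 × 2.5). At r = 0 this is √10.25 = 3.20. A paired t-test with n = 30 has noncentrality (1.68/3.20) × √30 = 2.87 and power 79.3%, which matches the stated 80%.

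**2. Chance of a stop.** With 9 degrees of freedom, two-sided p<0.001 requires |t| > 4.78. The noncentral t distribution gives:

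| r | SD of change | Power, n = 30, effect 1.68 | n for 80% power | P(stop), effect 1.68 | P(stop), effect 2.81 |
|---|---|---|---|---|---|
| 0 | 3.20 | 79.3% | 31 | 2.0% | 10% |
| 0.5 | 2.29 | 97.3% | 17 | 5.6% | 31% |
| 0.7 | 1.80 | 99.9% | 12 | 12.6% | 58% |
| 0.8 | 1.50 | >99.9% | 9 | 23.2% | 80% |

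A stop becomes likely only where far fewer than 30 subjects would answer the primary question. At the planned effect and r = 0, the expected number of subjects forgone is at most 0.0197 × 20 = 0.4.

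**3. Type I error.** The upper bound is 0.05 + 0.001 = 0.051. Simulation under no effect (8,000,000 trials) gives 0.0506. The statement in Section 2.6 that the final level needs no adjustment is correct for practical purposes.

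**4. The primary estimate.** Simulation of the written rule at effect 1.68 (6,000,000 trials per case), and of continuing to 30 after a crossing (8,000,000 per case):

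| r | Mean estimate ÷ truth, stopped at 10 | 95% coverage, stopped | Ratio if continued to 30 | Coverage if continued |
|---|---|---|---|---|
| 0 | 2.06 | 22% | 1.35 | 82% |
| 0.5 | 1.62 | 59% | 1.21 | 87% |
| 0.7 | 1.39 | 80% | 1.13 | 90% |
| 0.8 | 1.26 | 89% | 1.09 | 92% |

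The largest inflation belongs to the case that arises 2% of the time. Over all trials, stopped or not, the mean estimate is 1.70 to 1.75 against a truth of 1.68 (1.70/1.68 = 1.01; 1.75/1.68 = 1.04). Overall coverage across both effects is 93.5% to 95.0%. Continuing reduces the conditional bias but does not remove it.

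**5. The other aims after a stop.** The half-width of a 95% interval for a mean change is t(0.975, n−1)/√n in SD units: 0.72 with 10 and 0.37 with 30. Power for an illustrative 0.5 SD change is 29% with 10 and 75% with 30; if 5 or 10 more subjects under way complete, it is 44% or 56%. The chance of seeing at least one event with a true rate of 5% is 1 − 0.95¹⁰ = 40% or 1 − 0.95³⁰ = 79%.

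**6. What continuing would cost.** Each subject has a biopsy and a clamp at Visits 3 and 18 and an exercise test at Visits 2 and 16. Twenty further subjects mean up to 40 biopsies, 40 clamps and 40 maximal exercise tests, plus 12 weeks of drug each. Section 5.3 classes the research as above minimal risk.

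**The case for a change.** The case for an advisory rule is respectable. The wording is an obligation, it rests on one endpoint, and the DSMB could use discretion. Repeated measurements on one person are usually positively correlated, so 2% is probably the low end. If a stop did occur, the loss of precision in step 5 is real. Continuing would cost nothing in type I error (about 0.050 against 0.051), and the final test would still be significant in at least 98.1% of trials that crossed. The edit would be a few sentences.

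All of this stands as description, but it does not show that the rule gives a wrong result. The secondary and safety aims have no stated power or precision target, so the planned sample for them is simply the number chosen for the clamp endpoint. The 0.5 SD change is an illustration, not a protocol assumption. The trigger also has no direction, so it stops the trial for significant worsening as well. Turning the whole rule into a referral would weaken that protection. In an open-label study a fixed rule also has the merit that nobody who has seen the data decides whether it applies.

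Two side issues remain. Section 2.2.2 describes five subjects on an earlier combined regimen and three on a step-up, whereas the Synopsis and Section 1.4 describe a single regimen; who counts toward the ten is not stated. Section 3.1 says twenty subjects, against 30 elsewhere; with 20, the power comparison in step 5 becomes 29% against 56%. These passages must be reconciled as housekeeping, but neither bears on whether the stop should bind.

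**Conclusion.** The concern reads the text correctly but calls for no change. The stop is mandatory, prespecified and strict, and the error rate and overall coverage stay close to nominal. At the planned effect it takes hold in 2.0% of trials under the assumption that reproduces the stated power, and in 6% to 23% if r is 0.5 to 0.8. If the effect were the full 2.81, the range would be 10% to 80%.

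The choice after a crossing is between fuller data on aims with no stated target and sparing up to 20 people invasive procedures and study drug. The sponsor chose the second, which is reasonable. If the trial does stop early, a careful analyst would report that the primary estimate comes from a stopped trial and is likely to be too high, and would give the other endpoints with their wide intervals.

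These figures assume normally distributed changes, a two-sided test, no dropout and the listed values of r. The number of subjects under way at the look is not given; any who complete would soften the loss.

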3. HUMAN SUBJECTS

3.1 SUBJECT POPULATION

The anticipated age range for the study population will be 18-60 years of age based upon the target disease population. Twenty overweight/obese subjects ($BMI \geq 30$ kg/m²) with any ethnic background who have a confirmed diagnosis of hypertension and meet waist circumference criteria will be eligible for enrollment. All subjects must provide written informed consent prior to participation.

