1.4 SIGNIFICANCE

Important vasoprotective effects of inorganic nitrates and nitrites have been reported during the past decade, as evidenced by reduced BP, vascular inflammation and endothelial dysfunction. More recent findings suggest that inorganic nitrate and nitrite therapy may be involved in the regulation of glucose-insulin homeostasis. This proposal hypothesizes that oral supplementation with sodium nitrite will result in improvement in insulin sensitivity, reduction in BP, and improvement in endothelial and mitochondrial function, arterial stiffening, and microvascular inflammation, in overweight/obese adult subjects with metabolic syndrome and hypertension with limited toxicity in the dose proposed. First, we utilize a combination of powerful *in vivo* techniques (hyperinsulinemic euglycemic clamp, pharmacokinetic testing, muscle biopsy and platelet

analysis of mitochondrial function, cardiorespiratory fitness and various vascular function studies). Second, this is the first human study to investigate the inorganic nitrate or nitrite effects (in any form) on insulin sensitivity in any subject population. Additionally, this study is the first to design inorganic nitrite capsules for cardiovascular applications.

This study is an open-label, single-center non-randomized drug treatment study of overweight adults with metabolic syndrome and hypertension.

Adults (N=30) who fulfill the inclusion and exclusion criteria will be treated with 40 mg ¹⁴N sodium nitrite three times daily or TID (once in the morning and again in the early afternoon and again in the evening).

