2.2 DETAILED DESCRIPTION OF STUDY DESIGN

Potential subjects will undergo a screening visit to determine that eligibility requirements are met prior to being enrolled in the study. Subjects who meet the Inclusion Criteria, none of the Exclusion Criteria, and prior to receiving the study drug will be scheduled within 4 weeks of screening for baseline assessments. The study population (n=30) will receive oral sodium nitrite as follows:

Drug: oral formulation of sodium nitrite 20 mg or 40 mg capsules, for a dose of 40 mg three times daily or TID (once in the morning and again in the early afternoon and again in the evening).

Subjects will complete a 12-week outpatient treatment period. During the treatment period, subjects will be evaluated at weekly intervals. Throughout the study period, subjects will be asked to remain diligent in recording the exact date and time of study drug dosing with any associated symptoms.

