Chronic dietary supplementation of inorganic sodium nitrate in obese, hypertensive, insulin resistant mice lacking the gene for endothelial NO synthase (eNOS)²⁰ was studied. With a 10 week treatment of a modest dose of sodium nitrate of 0.1 mmol/kg/day (8.5 mg/kg/day) in the drinking water, significant reductions in blood pressure, fasting blood glucose, HbA1C, and proinsulin to insulin ratio were demonstrated, indicating reduced demands on the β-cell for insulin secretion.

Sodium nitrate drug is considered a source of nitrite through salivary nitrate reduction (rise in plasma nitrite after single oral sodium nitrate dose - see attached Fig 2A attached). Despite the plasma nitrite rise following a single oral sodium nitrate dose, we recently demonstrated in our phase I PK/PD study in 10 normal volunteers that no persistent blood pressure reduction with sodium nitrate 1,000 mg (see attached Fig 3A). In contrast, in the same phase I PK/PD study in 10 normal volunteers, we showed blood pressure decline in systolic, diastolic and mean arterial pressures over 3 hours with sodium nitrite 20 mg (Fig 3B). The oral sodium nitrite half-life was about 40-minutes and the effects of nitrite only lasted ≤6 hours. This was demonstrated by the plasma nitrite levels returning to baseline levels between 3 and 6 hours after nitrite dosing (i.e. the drug was given and gone out of the circulation within 6 hours). Specifically, mean baseline (pre-nitrite dosing) blood nitrite concentrations were 0.11 micromolar with a peak at 30 minutes of 5.5 micromolar, and return to baseline levels between the 3- (0.18 micromolar) and 6-hour (0.11 micromolar) monitoring time points (Fig 2B). In addition, there were no serious adverse events when these normotensive individuals received sodium nitrite including our 2 safety endpoints of methemoglobin levels and mean arterial pressure.

Additionally, we demonstrate lack of blood pressure lowering in our first 5 subjects on this current protocol's combined regimen of sodium nitrate 1,000 mg daily and sodium nitrite 20 mg BID during 2-hour post-dose BP monitoring at baseline vs. 12 weeks post (see attached Fig 1A), weekly seated blood pressures (Fig 1B) or 24-hour ambulatory blood pressures (ABP) at baseline vs. 12 weeks post (Fig 1C) and possible concern the sodium load within the 1,000 mg sodium nitrate dose may be blunting any potential BP effect.

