Based on the above PK and the differential BP effects with single doses of sodium nitrate vs. nitrite, the published 10-week oral nitrite trial and preliminary findings in this combined trial, we propose to remove sodium nitrate, which is the second potential depot of nitrite. Therefore, we need to administer a greater nitrite load since the previous two sources combined (sodium nitrate and nitrite) in the first 5 subjects of this study did not result in any BP lowering (Fig 1A-C). Similar to our prior dosing modification (when we titrated from sodium nitrite 20 mg once daily to 20 mg twice daily), we propose a step-up dosing in the first 3 subjects enrolled whereby we will begin with sodium nitrite 20 mg TID daily and after 2 weeks on this dosing and if no SAE, increase to 40 mg TID for the remaining 10 weeks of the study, given the PK of the drug and to induce blood pressure lowering in our hypertensive subjects. After three subjects have completed this regimen, then we propose that from the start, all remaining subjects start on sodium nitrite 40 mg TID and continue for all 12 weeks.

Although we are increasing the dose/frequency of sodium nitrite, since we are discontinuing sodium nitrate (which is reduced to nitrite in our body as was confirmed in our Phase I PK study), we are continuing our in-person safety monitoring visits to assess for adverse events at every other week. We will continue alternating every other week phone visits to assess compliance and for adverse events. Our two safety outcomes are methemoglobin by non-invasive co-oximetry and mean arterial pressure (MAP) obtained through 3 automated resting BP measurements 30-45 min following morning nitrite dosing and averaging the final 2 of 3 MAPs.

Based on the Joint FAO/WHO ADI for sodium nitrate and nitrite, the above DASH diet patterns, and the recently observed human and rodent effects of nitrate and nitrite on blood pressure and

glucose homeostasis, including our PK/PD trial of single doses of oral nitrate and nitrite, the existing inhaled nitrite trial, and this open label trial safety and lack of BP reduction findings following a total of 5 subjects' completion, the study investigators believe that a safe and likely therapeutically effective dose of sodium nitrite will be 40 mg three times daily (~1.26 mg/kg body weight per day for a 95 kg subject). Our sodium nitrite dose selection is equivalent to 12.6 times the ADI.

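### Section 3.1 gives the enrolment as twenty; every other statement of the sample size, including the power statement, says 30

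*Combined protocol and SAP*

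**What the plan says.** Section 3.1, which describes who is to be enrolled, gives the number as "Twenty overweight/obese subjects".

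The other statements of sample size give 30:

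- Synopsis, study design: "The study population (n=30) will receive oral sodium nitrite for 12 weeks". A separate synopsis line for the planned sample size also gives 30.
- Section 1.4: "Adults (N=30) who fulfill the inclusion and exclusion criteria will be treated with" the study drug.
- Section 2.2: "The study population (n=30) will receive oral sodium nitrite as follows".
- Section 2.6: "This would provide 80% power to detect this conservatively-estimated smaller effect size in 30 subjects at a p value of 0.05".

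Section 2.6 bases its power statement on an expected improvement of about 1.68 mg/min/kg FFM in insulin-stimulated glucose uptake. This is 60% of the change seen in 25 people after diet and exercise (6.70, SD 2.0, to 9.51, SD 2.5). The planned analysis is "Repeated measures ANOVA with visit (pre-, post-treatment) as the within-subject effect". The section gives no pre/post correlation, SD of change, sidedness or dropout allowance.

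**The concern.** The enrolment section and the statistical section name different sample sizes, and both are current text. Section 3.1 does not describe twenty as a minimum, a first stage or the number expected to be evaluable. The only interim look comes after the 10th subject, and section 3.1 does not refer to it.

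The enrolment number determines when recruitment ends and which sample the power claim covers. It also sets how many people undergo two muscle biopsies and two 4-hour clamps. If recruitment stopped at twenty on the strength of section 3.1, the trial would have two-thirds of the sample for which 80% power is stated.

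**Working it through.** **Inputs.** All are from section 2.6 unless marked as assumed.

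- Mean change: 0.6 × (9.51 − 6.70) = 0.6 × 2.81 = 1.686, which agrees with the stated 1.68. I use 1.68.
- SD before treatment s₁ = 2.0; SD after treatment s₂ = 2.5.
- Significance level 0.05. Two-sided is assumed.
- Pre/post correlation ρ: not given; 0, 0.3 and 0.5 are assumed.
- Dropout: no allowance is given; none is assumed.

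**Method.** A repeated measures ANOVA with two visits and one group is equivalent to a paired t-test. The SD of change is

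SD_Δ = √(s₁² + s₂² − 2ρs₁s₂) = √(4 + 6.25 − 10ρ) = √(10.25 − 10ρ).

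Power comes from the noncentral t distribution with n − 1 degrees of freedom and noncentrality (1.68 / SD_Δ) × √n.

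**Step 1: reproduce the plan's figure.** With ρ = 0, SD_Δ = √10.25 = 3.202. For n = 30 the noncentrality is (1.68 / 3.202) × √30 = 2.87 and power is 79.3%, which agrees with the stated 80%. An independent-samples calculation with pooled SD √(10.25 / 2) = 2.264 and 30 per group gives 80.7%. The protocol does not say which method was used, but either one leads to 80% at 30.

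**Step 2: repeat at 20.** With ρ = 0 the noncentrality is (1.68 / 3.202) × √20 = 2.35 and power is 60.5%. The independent-samples version with 20 per group gives 62.8%.

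**Step 3: vary the correlation.**

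| Assumed ρ | SD_Δ | Power, n = 30 | Power, n = 20 |
|---|---|---|---|
| 0 | 3.202 | 79.3% | 60.5% |
| 0.3 | 2.693 | 91.0% | 75.4% |
| 0.5 | 2.291 | 97.3% | 87.5% |

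**Step 4: use only what the plan's 80% implies.** Exactly 80% at n = 30 requires SD_Δ = 3.174, that is ρ = (10.25 − 3.174²) / 10 ≈ 0.02. With that SD_Δ, power at n = 20 is 61.3%. Correlations of 0.3 or 0.5 do not fit the plan's own statement, since they would give 91% or 97% at 30. They are sensitivity values.

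**Step 5: what twenty would need for 80%.** SD_Δ must be 2.544 or less, so ρ must be at least (10.25 − 2.544²) / 10 ≈ 0.38.

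**Step 6: sensitivity to the post-treatment SD.** The 2.5 is borrowed from the diet-and-exercise data. If s₂ equalled the pre-treatment SD of 2.0 (an assumption), then SD_Δ = √(8 − 8ρ). For ρ = 0 / 0.3 / 0.5, power at 20 would be 71.2% / 85.3% / 94.5%, and at 30 it would be 88.2% / 96.4% / 99.4%. The correlation needed for 80% at 20 falls to (8 − 2.544²) / 8 ≈ 0.19.

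**The case against.** The strongest reply is that this is a leftover word with little consequence. The synopsis has a line given over to the planned sample size, the statistical section rests on 30, and four parts of the protocol agree against one descriptive paragraph. No endpoint, analysis or visit depends on the word, and a reader who saw all the passages would take 30 as intended. The arithmetic in section 2.6 is also sound, so this is an inconsistency and not a miscalculation. The loss of power is doubly conditional: it arises only if twenty is followed, and only if the pre/post correlation is low. At a correlation of 0.5, twenty subjects would still exceed 80%.

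Most of that is right and limits the weight of the point. It does not remove the conflict. Section 3.1 is current text on who is enrolled, and nothing in the protocol subordinates it to the synopsis. The reliance on a favourable correlation also works against twenty: the protocol states none, and the value implied by its own 80% at 30 is close to zero.

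**Conclusion.** The point holds as an internal inconsistency in the sample size. Section 3.1 says twenty where the rest of the protocol says 30, and the 80% power statement is valid for 30 only. On the basis implied by the plan's own figure, power at twenty would be about 61%. Over assumed correlations of 0 to 0.5 it runs from 60.5% to 87.5% with a post-treatment SD of 2.5, and from 71.2% to 94.5% with 2.0. These figures assume a two-sided test and no dropout.

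The 80% at 30 is not in error, and no shortage of power at 30 has been shown. This is one outlying number that should be corrected because of where it stands.

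**What to change.** Change the number in section 3.1 so that it agrees with the 30 on which section 2.6 rests. This is one word, and against the planned 30 it adds no subjects, visits or data.

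Two clarifications are worth making in the same edit, although the correction does not depend on them:

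- In section 2.6, state the SD of change or the pre/post correlation behind the 80%, and the method used. One or two sentences are enough.
- Say whether the five people treated earlier with combined nitrate and nitrite count towards the 30. Section 2.2.2 refers to "lack of blood pressure lowering in our first 5 subjects on this current" protocol's combined regimen, and says that the two sources "in the first 5 subjects of this study did not result in any BP lowering". The synopsis and sections 1.4 and 2.2 tie the 30 to sodium nitrite alone, which on a plain reading leaves those five out. One sentence would settle it.
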